## 6.2.2.3.1 Dose De-escalation Rules for Adult Subjects

During the Phase 1b part, up to 6 subjects will be enrolled in Cohort 1A and receive one to five treatment cycles of blinatumomab at a target blinatumomab dose of 9-28  $\mu$ g/day CIVI, as described in Section 6.2.1. Cohort 2 may open as soon as 5 subjects have completed the DLT observation period with no DLTs, or when 6 subjects have completed the DLT observation period with 0-1 DLT. If  $\geq$  2 subjects experience a DLT during the DLT observation period while receiving 9  $\mu$ g/day during Cohort 1A, the cohort will be closed and Cohort 1C will open at a de-escalated dose level of blinatumomab.

If ≥ 2 subjects experience a DLT during the DLT observation period while receiving 28 μg/day during Cohort 1A, the cohort will be closed and Cohort 1B will open at a de-escalated dose level of blinatumomab. Further, if 1 subject experiences a DLT at 9 μg/day and 1 subject experiences a DLT at 28 μg/day during the DLT observation period in Cohort 1A, the cohort will be closed and Cohort 1D will open at a de-escalated dose level of blinatumomab.

In Cohort 1B, up to 6 subjects will receive a target blinatumomab dose of 9-24  $\mu$ g/day CIVI. Cohort 2 may open as soon as 5 subjects have completed the DLT observation period with no DLTs, or when 6 subjects have completed the DLT observation period with 0-1 DLT. If  $\geq$  2 subjects experience a DLT during the DLT observation period during Cohort 1B, irrespective of dose level, the cohort will be closed and Cohort 1D will open at a de-escalated dose level of blinatumomab.

In Cohort 1C, up to 6 subjects will receive a target blinatumomab dose of 6-28  $\mu$ g/day CIVI. Cohort 2 may open as soon as 5 subjects have completed the DLT observation period with no DLTs, or when 6 subjects have completed the DLT observation period with 0-1 DLT. If  $\geq$  2 subjects experience a DLT during the DLT observation period during Cohort 1C, irrespective of dose level, the cohort will be closed and Cohort 1D will open at a de-escalated dose level of blinatumomab.

### 6.2.2.3.2 Dose De-escalation Rules for Pediatric Subjects

Up to 6 subjects will be enrolled in Cohort P1 and receive one to five treatment cycles of blinatumomab at a target blinatumomab dose of 5-15  $\mu$ g/m²/day CIVI, as described in Section 6.2.1. If  $\geq$  2 subjects experience a DLT during the DLT observation period while receiving 5  $\mu$ g/m²/day during Cohort P1, the cohort will be closed and Cohort P3 will open at a de-escalated dose level of blinatumomab. If  $\geq$  2 subjects experience a DLT during the DLT observation period while receiving 15  $\mu$ g/m²/day during Cohort P1, the cohort will be closed and Cohort P2 will open at a de-escalated dose level of blinatumomab. Further, if 1 subject experiences a DLT at 5  $\mu$ g/m²/day and 1 subject experiences a DLT at 15  $\mu$ g/m²/day during the DLT observation period in Cohort P1, the

\* Subjects who achieve a complete remission (CR, defined as CR/CRh\*) within 2 induction cycles of treatment may receive consolidation cycles of blinatumomab (up to a maximum of 5 total induction and consolidation cycles, or disease progression, intolerable adverse event or withdrawal of consent)

Date: 20 March 2019 Page 45 of 122

cohort will be closed and Cohort P4 will open at a de-escalated dose level of blinatumomab.

In Cohort P2, up to 6 subjects will receive a target blinatumomab dose of 5-10 µg/m²/day CIVI. If ≥ 2 subjects experience a DLT during the DLT observation period during Cohort P2, irrespective of dose level, the cohort will be closed and Cohort P4 will open at a de-escalated dose level of blinatumomab.

In Cohort P3, up to 6 subjects will receive a target blinatumomab dose of  $3.75-15 \,\mu g/m^2/day \,CIVI$ . If  $\geq 2$  subjects experience a DLT during the DLT observation period during Cohort P3, irrespective of dose level, the cohort will be closed and Cohort P4 will open at a de-escalated dose level of blinatumomab.

In Cohort P4, up to 6 subjects will receive a target blinatumomab dose of  $3.75-10 \,\mu g/m^2/day \, CIVI$ . If  $\geq 2 \, subjects \, experience \, a \, DLT \, during the \, DLT \, observation period during Cohort P4, irrespective of dose level, further enrollment into the study will be suspended until further notice. Additional cohorts may be opened at the discretion of Amgen.$ 

In the expansion cohort, pediatric subjects will receive the dose selected from the Phase1 part (5-15 µg/m²/day) of blinatumomab.

Subjects who experience a DLT may re-start treatment at a reduced dose after the DLT has resolved and the investigator has consulted with an Amgen medical monitor.

Subjects who do not experience a DLT or meet other criteria for dose modification per Section 6.5 at the time a cohort is closed may continue treatment at a reduced dose after the investigator has consulted with an Amgen medical monitor.

The study design schema in the protocol synopsis further illustrates the dose de-escalation rules. Blinatumomab dose levels by cohort are described in Table 3.

e: 20 March 2019 Page 46 of 122

Product: Blinatumomab Protocol Number: 20130265 Date: 20 March 2019

	D 4	D	
Table 3.	Blinatumomab	Pediatric Dose I	Levels by Cohort

		Blinatumomab							
		Cyc Indu	Cycles 2 to 5: Induction and Consolidation a						
Part	Cohort	Day 1 to Day 7	Day 8 to Day 29	Day 1 to Day 29					
Phase 1b	P1	5 μg/m²/day CIVI	15 μg/m²/day CIVI	15 μg/m²/day CIVI					
Phase 1b	P2	5 μg/m²/day CIVI	10 μg/m²/day CIVI	10 μg/m²/day CIVI					
Phase 1b	P3	3.75 µg/m²/day CIVI	15 μg/m²/day CIVI	15 μg/m²/day CIVI					
Phase 1b	P4	3.75 µg/m²/day CIVI	10 μg/m²/day CIVI	10 μg/m²/day CIVI					

CIVI = continuous intravenous infusion.

## 6.2.2.4 Data Review Committee

A DRC will review safety data from each cohort in the Phase 1b part to determine if blinatumomab is safe and tolerable as defined by DLT criteria, taking into account a general benefit: risk assessment. PK data may be reviewed, if available. The DRC will meet to confirm the decision rules and recommendations summarized in Table 2 for adult subjects and Table 3 for pediatric subjects when any of the following criteria are met:

- 2 or more subjects have experienced a DLT in a cohort
- 5 or 6 subjects are enrolled in a cohort and all subjects have completed the 14-day DLT observation period

The DRC will consist of, at a minimum, members from the Amgen and Amgen Astellas Biopharma (AABP) study teams, including at least one clinician, one safety representative, and one investigator participating in the study who has recruited subjects into the cohort under review. Refer to Section 10.3.2 for more information on the scope of the DRC.

Adverse events in Appendix H and Appendix I which differ substantially in severity or tolerability compared to the currently known safety profile as determined by the DRC will be reviewed by the independent DSMB.

<sup>a Subjects who achieve a bone marrow response (blasts ≤ 5%) within 2 induction cycles of treatment may receive consolidation cycles of blinatumomab (up to a maximum of 5 total induction and consolidation cycles, or disease progression, intolerable adverse event or withdrawal of consent)

Date: 20 March 2019 Page 47 of 122

## 6.3 Dexamethasone Premedication

Premedication with dexamethasone is intended to prevent neurologic, CRS, and tumor lysis syndrome events associated with blinatumomab treatment.

Table 4 below summarizes dexamethasone use prior to blinatumomab treatment during different phases of the study. Please also refer to appropriate protocol sections for specific details as not all information is contained within Table 4. As clarification, the dexamethasone dosages referenced in the protocol are inclusive of the salt (eg, dexamethasone sodium phosphate).

Date: 20 March 2019 Page 48 of 122

**Table 4. Dexamethasone Premedication** 

Treatment Phase	Target Subject	Dexamethasone Dose	Comments
Pre-phase Therapy Prior to Start of Treatment	Mandatory if:  ■ Blast proportion in bone marrow is > 50%, OR ■ Peripheral blood blast count ≥ 15,000/µL  Recommended if:  ■ LDH indicates rapidly progressing disease, OR ■ Extramedullary high tumor load	Adults and Pediatrics:  Dexamethasone 10 mg/m²/day can be administered up to 5 days during screening, preferably IV. If indicated dexamethasone may be increased to an absolute maximum of 24 mg/day.	See protocol Section 6.3.1
Pre-dose Dexamethasone	All subjects	Adults: (prior to each treatment cycle and dose step)  Dexamethasone 20 mg IV within 1 hour prior to start of infusion in each treatment cycle, and within 1 hour prior to dose step.  Pediatrics: (prior to Cycle 1):  Dexamethasone 10 mg/m² oral or IV within 6-12 hours AND 5 mg/m² oral or IV within 30 minutes prior to the start of infusion.	See protocol Section 6.3.2
Infusion Interruption/Dose Modification Due to Adverse Event	Subjects with treatment interruption > 4 hours	Adults:  Dexamethasone 20 mg IV within 1 hour prior to restart of treatment.  Pediatrics:  Dexamethasone 10 mg/m² oral or IV within 6-12 hours AND 5 mg/m² oral or IV within 30 minutes prior to restart of treatment.	See protocol Section 6.5.1 and 6.3.2
In case of signs of cytokine release (CRS)	Subjects with signs of CRS	Adults:  Dexamethasone at a maximum dose of 8 mg, 3 times per day. Reduce step-wise over 4 days or as otherwise appropriate per investigator.  Pediatrics:  Dexamethasone at a total daily dose of at least 0.2-0.4 mg/kg/day, preferably IV (maximum 24 mg/day), divided into 3 doses per day for up to 3 days, then reduced step-wise by at least 25% per day over up to 4 days.	See protocol Section 6.5.1
Infusion Interruption/Dose Modification Due to Neurologic Events	Subjects with CNS-related adverse event	Adults:  Dexamethasone up to 24 mg/day for up to 3 days. Reduce step-wise over 4 days or as otherwise appropriate per investigator.  Pediatrics:  Dexamethasone at a total daily dose of at least 0.2-0.4 mg/kg/day, preferably IV (maximum 24 mg/day), divided into 3 doses per day for up to 3 days, then reduced step-wise by at least 25% per day over up to 4 days.	See protocol Section 6.5.2

Date: 20 March 2019 Page 49 of 122

## 6.3.1 Pre-phase Therapy Prior to Start of Blinatumomab Treatment

Premedication with dexamethasone is intended to prevent neurologic, CRS, and tumor lysis syndrome events associated with blinatumomab treatment. Please refer to Table 4 for pre-phase dosing instructions with dexamethasone.

Mandatory pre-phase therapy with dexamethasone is required prior to blinatumomab treatment if the following criteria are met:

- Proportion of blasts (determined by cytomorphology) is > 50%, OR
- Peripheral blood blast count ≥ 15,000/µL

Pre-phase therapy with dexamethasone is recommended prior to blinatumomab treatment for all subjects, particularly if in the opinion of the investigator:

- LDH indicates rapidly progressing disease, OR
- Signs of extramedullary disease show high tumor load

Pre-phase dexamethasone at a dose up to 10 mg/m²/day can be administered up to 5 days during screening, preferably IV. If clinically indicated, the dexamethasone dose can be increased to an absolute maximum dose of 24 mg/day.

If the subject received dexamethasone (up to 24 mg/day) for reasons other than pre-phase within 14 days prior to the start of screening, further pre-phase treatment with dexamethasone is not required. However, premedication with dexamethasone is required prior to start of infusion as described in Table 4 and Section 6.3.2.

It should be noted that in cases of ALL that are refractory to dexamethasone treatment, a preventative effect on CRS can still be achieved. If a subject is refractory to dexamethasone, a pre-phase is not mandatory, but dexamethasone up to a maximum dose of 24 mg/day should be administered at least for the first 2 days of treatment with step-wise reduction afterwards.

Subjects who should receive dexamethasone treatments of up to 24 mg/day and who have already received the mandatory premedication dose prior to blinatumomab infusion on cycle 1 day 1 may receive the remaining balance of dexamethasone up to a maximum of 24 mg/day.

Product: Blinatumomab

Date: 20 March 2019 Page 50 of 122

### 6.3.2 Pre-dose Dexamethasone Prior to Treatment Cycles and Dose Step

### 6.3.2.1 **Premedication for Adult Subjects**

Mandatory premedication with dexamethasone is required for the prevention of CRS resulting from blinatumomab prior to each treatment cycle and dose step:

- Dexamethasone 20 mg IV within 1 hour prior to start of infusion and
- Dexamethasone 20 mg IV within 1 hour prior to dose step

Dexamethasone premedication will also be required prior to restarting blinatumomab after an infusion interruption due to an adverse event (refer to Table 4 and Section 6.5.1.1).

### 6.3.2.2 **Premedication for Pediatric Subjects**

Mandatory premedication with dexamethasone is required for the prevention of CRS resulting from blinatumomab prior to cycle 1:

- Dexamethasone 10 mg/m^2 orally or IV 6 to 12 hours prior to start of infusion, AND
- Dexamethasone 5 mg/m^2 orally or IV within 30 minutes prior to start of infusion
- Dexamethasone premedication will also be required prior to restarting blinatumomab after an infusion interruption due to an adverse event (refer to Table 4 and Section 6.5.1.2).

### 6.4 **CSF Prophylaxis Before and During Blinatumomab Treatment**

Within 1 week (+ 3 days) prior to start of blinatumomab and following each treatment cycle (after bone marrow aspiration on day 29) a mandatory CSF prophylaxis consisting of an intrathecal regimen according to institutional or national guidelines will be administered (eg, methotrexate, cytosine arabinoside, dexamethasone). Intrathecal therapy during and after maintenance therapy will be left to the investigator's discretion.

In case of anticipated safety risks caused by lumbar puncture (eg, in case of thrombocytopenia), lumbar puncture and CSF prophylaxis may be omitted.

Product: Blinatumomab

Date: 20 March 2019 Page 51 of 122

6.5 Dosage Adjustments, Delays, Rules for Withholding or Restarting, **Permanent Discontinuation** 

### 6.5.1 Infusion Interruption/Dose Modification due to Adverse Events

### 6.5.1.1 **Adult Subjects**

Blinatumomab treatment will be interrupted until the following non-DLT events resolve to ≤ grade 1:

- Grade 3 or higher CRS, tumor lysis syndrome, and disseminated intravascular coagulation (DIC)/coagulopathy related to blinatumomab
- Grade 3 or higher clinically relevant neurologic event related to blinatumomab, as defined in Appendix I

In the event of a grade 3 or higher infection, blinatumomab will be interrupted until the infection is adequately controlled or resolved per the opinion of the investigator.

For interruptions or dose modifications due to neurologic events (as defined in Appendix I), see Section 6.5.2.

CTCAE grade 4 adverse events not defined solely based on laboratory parameters at least possibly related to blinatumomab will require permanent discontinuation of blinatumomab. Independent investigator assessment should be used to determine the risk:benefit for each individual subject to continue blinatumomab therapy with or without dose reduction or discontinue therapy for:

- Grade 4 adverse events that are numerically defined laboratory parameters
- All other grade 3 adverse events and clinically significant laboratory value changes

If the adverse event resolves to ≤ grade 1 within 1 week, blinatumomab may be restarted at the lower assigned dose level for the subject's assigned cohort for at least 7 days before increasing to the higher assigned dose level.

Restart of the infusion should be performed under supervision of the investigator. Before blinatumomab is restarted, premedication with dexamethasone must be administered as described in Table 4. The subject should be observed overnight for possible side effects after the restart.

In addition to the events described above, the dose may be temporarily or permanently reduced to the lower assigned dose level for the subject's assigned cohort if, by the investigator's judgment, it is necessary for safety reasons. After at least 7 days of dosing at the lower assigned dose level, the dose may be increased to the higher assigned dose level, or treatment may be continued at the lower assigned dose level

Product: Blinatumomab Date: 20 March 2019

after consultation with an Amgen medical monitor. The subject will continue to be treated at the adjusted blinatumomab dose and evaluated in the originally assigned cohort.

During the Phase 2 part only, if the interruption after an adverse event is 7 days or less, the same cycle will be continued. The infusion duration before and after an interruption should total 28 days per treatment cycle. If an interruption due to an adverse event is greater than 7 days, a new cycle will start. In addition, an incomplete treatment cycle with a treatment duration of less than 2 weeks will not be counted as an evaluable cycle for the primary endpoint and will have to be repeated (eg, if cycle 1 was interrupted on day 8 for more than 7 days, the next cycle will be denoted as cycle 1.1 and the same assessments will be performed as in cycle 1). For cycle 1.1, subjects will be started at the lower assigned dose for the subject's assigned cohort for the first 7 days of dosing followed by a dose step to the higher assigned dose level beginning at cycle 1.1 day 8 and continuing for the remainder of cycle 1.

An infusion interruption of more than 2 weeks due to an adverse event related to blinatumomab will lead to permanent discontinuation of treatment. In case of logistical difficulties, restart of treatment can be postponed for up to 7 additional days without resulting in permanent treatment discontinuation.

Any infusion interruption or dose modifications due to adverse event will be recorded in the eCRF.

Infusion interruption/dose modification guidelines for adult subjects in the expansion cohort will be the same as described above.

### 6.5.1.2 **Pediatric Subjects**

Blinatumomab treatment will be interrupted until the following events resolve to ≤ grade 1:

- Grade 2 or higher CRS, tumor lysis syndrome, and DIC/coagulopathy related to blinatumomab
- Grade 2 clinically relevant neurologic event related to blinatumomab, as defined in Appendix I
- Any grade 3 or higher clinically relevant adverse event related to blinatumomab

CTCAE grade 4 adverse events not defined solely based on laboratory parameters at least possibly related to blinatumomab will require permanent discontinuation of blinatumomab. Independent investigator assessment should be used to determine the

Page 52 of 122

Product: Blinatumomab

Date: 20 March 2019 Page 53 of 122

risk:benefit for each individual subject to continue blinatumomab therapy with or without dose reduction or discontinue therapy for:

Grade 4 adverse events that are numerically defined laboratory parameters

 All other grade 3 adverse events and clinically significant laboratory value changes

If the adverse event resolves to  $\leq$  grade 1, blinatumomab may be restarted at the lowest starting dose of the dose cohort for at least 7 days before increasing to a maximum of 15  $\mu$ g/m²/day.

Laboratory assessments will be performed during cycle 1 on days 1 and 2 for the monitoring of tumor lysis syndrome. If a CRS, tumor lysis syndrome, or DIC are observed during week 1, dose modifications will be made as outlined in Table 5. If this dose reduction occurs during cycle 1, the DLT observation period will be extended for an additional 7 days.

Table 5. Treatment Modification for Reversible CRS, Tumor Lysis Syndrome, and DIC

Current Dose	Week 1	Week 2 (Day 8)	Week 3-4 (Day 15)
5 μg/m²/day	3.75 μg/m²/day	5 μg/m²/day	15 μg/m²/day
15 μg/m²/day	5 μg/m²/day	15 μg/m²/day	15 μg/m²/day
10 μg/m²/day	5 μg/m²/day	10 μg/m²/day	10 μg/m²/day

Restart of the infusion should be performed under supervision of the investigator. Before blinatumomab is restarted, premedication with dexamethasone must be administered as described in Table 4. The subject should be observed overnight for possible side effects after the restart.

In addition to the events described above, the dose may be temporarily or permanently reduced to the lower assigned dose level, if, by investigator's judgment, it is necessary for safety reasons. After at least 7 days of dosing at the lower assigned dose level, the dose may be increased to the highest assigned dose level or treatment may be continued at the lowest assigned dose level after consultation with an Amgen medical monitor. This does not apply for neurologic events as outlined in Appendix I

If the interruption after an adverse event is less than 7 days, the same cycle will be continued. The infusion duration before and after an interruption should total 28 days per treatment cycle. If an interruption due to an adverse event is greater than 7 days, a new cycle will start. In addition, an incomplete treatment cycle with a treatment duration

Product: Blinatumomab

Date: 20 March 2019 Page 54 of 122

of less than 2 weeks will not be counted as an evaluable cycle for the primary endpoint and will have to be repeated (eg, if cycle 1 was interrupted on day 8 for more than 7 days, the next cycle will be denoted as cycle 1.1 and the same assessments will be performed as in cycle 1). For cycle 1.1, subjects will be started at 5 µg/m²/day for the first 7 days of dosing followed by a dose step to 15 μg/m^2/day beginning at cycle 1.1 day 8 and continuing for the remainder of cycle 1.

An infusion interruption of more than 2 weeks due to an adverse event related to blinatumomab will lead to permanent discontinuation of treatment. In case of logistical difficulties, restart of treatment can be postponed for up to 7 additional days without resulting in permanent treatment discontinuation.

Any infusion interruption or dose modifications due to adverse event will be recorded in the eCRF.

Infusion interruption/dose modification guidelines for pediatric subjects in the expansion cohort will be the same as described above.

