### 6.2.2.2 DLT Observation Period

The time for the DLT assessment will be the first 14 days of treatment based on the observation that most adverse events are usually observed within a few days of treatment initiation and dose step. If the dose modification per Table 5 is followed, time for the DLT assessment will be the first 21 days. An observed DLT will be attributed to the blinatumomab dose level administered at the time at which the DLT occurred.

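### The pediatric cycle 1.1 doses and the Table 5 row for 5 µg/m²/day contradict the assigned doses of de-escalation cohorts P2 to P4 (internal inconsistency, minor)

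*Protocol*

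**What the plan says.** All doses below are in µg/m²/day. Protocol Section 6.2.2.3.2 and Table 3 assign P1 5-15, P2 5-10, P3 3.75-15 and P4 3.75-10. The same section gives the pediatric expansion dose as 5-15, the dose selected from Phase 1.

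Section 6.5.1.2 contains three rules for resuming treatment in children:

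- **Cycle 1.1.** A cycle with less than 2 weeks of treatment must be repeated, for example when it was interrupted early for more than 7 days. The repeat starts at 5 "for the first 7 days of dosing followed by a dose step to 15". No cohort is mentioned.
- **General restart.** After an adverse event resolves, "blinatumomab may be restarted at the lowest starting dose of the dose cohort" and held there "for at least 7 days before increasing to a maximum of 15".
- **Table 5** ("Treatment Modification for Reversible CRS, Tumor Lysis Syndrome, and DIC"). For an event in week 1, a child on 5 goes to 3.75, then 5, then 15. A child on 15 goes to 5, 15, 15, and a child on 10 goes to 5, 10, 10. SAP Table 2 has the same three rows.

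Two further provisions bear on the DLT evaluation. Section 6.5.1.2 says: "If this dose reduction occurs during cycle 1, the DLT observation period will be extended for an additional 7 days". Section 6.2.2.2 says: "If the dose modification per Table 5 is followed, time for the DLT assessment will be the first 21 days".

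**The concern.** The cohort fixes a child's dose pair, but two mandatory rules in Section 6.5.1.2 do not refer to the cohort. The parallel adult rule in Section 6.5.1.1 does: cycle 1.1 there uses the lower and then the higher dose of the subject's own cohort.

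P2 opens only after at least two children in P1 have had DLTs at 15, and P3 only after at least two have had DLTs at 5. Followed literally, cycle 1.1 returns a child who has just had a treatment interruption to the level the cohort was opened to avoid: 15 in P2 and 5 in P3. In P4 both doses are too high.

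Table 5 raises a second question. For a P2 child its step to 15, labelled day 15, falls inside the DLT window once that window is extended to 21 days. P2 closes on two or more DLTs at either dose level, so a DLT at 15 would count toward closing a cohort meant to test 10.

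**Working it through.** The plan gives no figure to reproduce here. The check sets the written doses against the assigned ones.

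**Cycle 1.1.** The inputs are the assigned doses (Table 3) and the written doses of 5 for 7 days, then 15 (Section 6.5.1.2). The 28-day total, assuming a full cycle without further interruption, is 7 × lower + 21 × higher. As written this is 7 × 5 + 21 × 15 = 350 µg/m² in every cohort.

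| Cohort | Assigned | Assigned total (µg/m²) | Written ÷ assigned total | Lower dose ratio | Higher dose ratio |
|---|---|---|---|---|---|
| P1 | 5-15 | 35 + 315 = 350 | 1.00 | 1.00 | 1.00 |
| P2 | 5-10 | 35 + 210 = 245 | 1.43 | 1.00 | 15/10 = 1.50 |
| P3 | 3.75-15 | 26.25 + 315 = 341.25 | 1.026 | 5/3.75 = 1.33 | 1.00 |
| P4 | 3.75-10 | 26.25 + 210 = 236.25 | 1.48 | 1.33 | 1.50 |

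**Table 5 in P2.** In the first week of cycle 1, P1 and P2 children are both on 5, so both follow the row 3.75, 5, 15. That ends at the assigned dose in P1 (15) and above it in P2 (15 against 10). A P2 child already on 10 follows the row for 10 and ends correctly at 10.

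**Table 5 in P4.** A P4 child is normally on 3.75 in the first week and does not meet the row for 5. If cycle 1.1 is started at 5 as written, and its first week counts as week 1 for Table 5 (an assumption), an event in that week leads to the same row. The child then ends at 15 against an assigned 10.

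**Size of the Table 5 excess in P2.** Compare the row as written with the same row ending at 10. If the table's days are cycle days, the difference is 14 days × (15 − 10) = 70 µg/m². If its weeks count from restart, with k days already given at 5 and 28 infusion days in all, the difference is (14 − k) × 5 = 70 − 5k. That is 70 at k = 0 and 35 at k = 7.

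This is not an excess over P2's planned total of 245. The written row totals 5k + 26.25 + 35 + 15 × (14 − k) = 271.25 − 10k, which is below 245 from k = 3. The conflict is in the dose level, not necessarily in the total.

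**Overlap with the DLT window.** With the days as labelled, days 15 to 21 (7 days) are at 15. Counted from restart, the step falls on treatment day 15 + k. That is inside 21 days for k up to 6, with 7 − k days at 15; interruption days are not counted.

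**The case against.** The strongest reply is that nothing live is affected. The protocol already names 5-15 as the selected pediatric dose, and both rules match 5-15 exactly. That stands and limits the weight of the point. It does not remove the point, because P2 to P4 remain in the current text with mandatory instructions that contradict them. Nor can Table 5 be read as written for P1 alone: it has a row for 10, a dose assigned only in P2 and P4.

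Other provisions narrow the route. A child with a DLT may restart at a reduced dose after consultation with the medical monitor. Related grade 4 events not defined solely by laboratory values end treatment, as do related interruptions of more than 2 weeks, apart from a logistical allowance. Neurologic events restart at the cohort's lower dose without escalation. The investigator may also reduce the dose for safety. None of these says that the assigned dose overrides the cycle 1.1 sentence or Table 5.

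A reader might infer more than the documents support:

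- **That the cap of 15 in the general restart rule is also an error.** It is a permissive ceiling in a sentence that starts from the cohort's own lowest dose. It allows more than 10 in P2 and P4 but does not order it.
- **That stepping P3 and P4 children down to 5 (rows for 15 and 10) is wrong because their lower dose is 3.75.** This is a specific reduction, of 67% from 15 or 50% from 10, and stays below the cohort maximum. The level is a clinical choice.
- **That the DLT evaluation would be corrupted.** Section 6.2.2.2 says: "An observed DLT will be attributed to the blinatumomab dose level administered at the time at which the DLT occurred". Section 6.2.2.4 adds: "The DRC will meet to confirm the decision rules and recommendations". The off-cohort dose would be visible when the decision is made, so a mistaken closure of P2 is possible but not shown.

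**Conclusion.** The point holds as a minor internal inconsistency in two places. The cycle 1.1 sentence contradicts the assigned doses of P2 (upper), P3 (lower) and P4 (both), by 50% at the upper dose and 33% at the lower. The Table 5 row for 5, and its copy in the SAP, takes a P2 child to 15 instead of 10; a P4 child could meet the same row through cycle 1.1 as written.

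The dose ratios come directly from the documents. The cycle totals (+43%, +2.6% and +48%) rest on a full 28-day cycle 1.1, and the 35 to 70 µg/m² for Table 5 is measured against a corrected row. P1 and the expansion cohort are consistent. The error acts only if P2, P3 or P4 is in use. Sample size, endpoints, analysis and the selected 5-15 dose are not affected.

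**What to change.** Make two changes:

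1. In Section 6.5.1.2, word the pediatric cycle 1.1 sentence as in the adult section: the lower assigned dose of the subject's cohort for 7 days, then the higher assigned dose.
2. In Protocol Table 5 and SAP Table 2, end the row for 5 at the cohort's higher assigned dose: 10 in P2, and 15 in P1 and the expansion cohort.

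Replacing the cap of 15 in the general restart sentence with the cohort's higher assigned dose is an optional clarification. The rows for 15 and 10 need no change.

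The cost is one sentence, one table row and its copy in the SAP, plus a second sentence if the optional wording is adopted. No new schedule, stopping rule or analysis is needed.
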